Principal Investigator: [name] Print/Type Name

Signed: _____ Date: _____

STUDY SUMMARY

Title: Adaptive tyrosine kinase inhibitor therapy in patients with advanced progressive thyroid cancer.

Précis: This is a randomized phase II clinical trial to evaluate the efficacy and tolerability of tyrosine kinase inhibitor (TKI) therapy through adaptive (intermittent) versus conventional (continuous) dosing schedule in patients with differentiated thyroid cancer (DTC) or medullary thyroid cancer (MTC).

Objectives: **Primary objective:**

- To evaluate the efficacy and tolerability of TKI therapy (Lenvatinib or Sorafenib for DTC; Cabozantinib or Vandetanib for MTC) through adaptive (intermittent) versus conventional (continuous) regimen.

Secondary objective:

- To evaluate response and survival of TKI therapy (Lenvatinib or Sorafenib for DTC; Cabozantinib or Vandetanib for MTC) through adaptive (intermittent) versus conventional (continuous) regimen.

Exploratory objective:

- To determine predictive biomarkers of TKI response.

Endpoint: **Primary endpoint:**

- Time to TKI treatment discontinuation due to progressive disease, intolerability, or disease-related death at 2 years.

Secondary endpoints:

- Overall response rate
- Progression free survival
- Overall survival

Exploratory endpoints:

- Determine predictive biomarkers of TKI response

Population: Patients with advanced progressive 131I-refractory DTC or MTC will be enrolled to this study. Forty-five patients responding to TKI therapy (defined as $\geq 50\%$ drop in tumor marker level within the first two months of treatment) will be randomized to receive TKI therapy either through adaptive (intermittent) or conventional (continuous) regimen.

Phase: Randomized phase II clinical trial

Number of Sites enrolling participants: 1 (Moffitt Cancer Center)

Description of Study Agent:

[figure not shown]
- All patients will start receiving standard of care treatment: Lenvatinib 24 mg daily or Sorafenib 400 mg twice daily with DTC; Cabozantinib 140 mg daily or Vandetanib 300 mg daily with MTC. Doses will be adjusted as needed due to toxicity or drug tolerance in both arms.
- Patients in the conventional therapy regimen will receive continuous treatment at the indicated dose until disease progression or development of intolerability.

- Patients in the adaptive therapy regimen will receive TKI therapy in cycles: continuous treatment at the indicated dose until the patients' tumor marker (thyroglobulin in DTC patients; calcitonin or CEA in MTC patients) drops by $\geq 50\%$ from the level at the time of enrollment ("baseline" level). Only tumor markers that meet inclusion criteria at baseline can be used for randomization and adaptive therapy purposes. A new cycle of TKI treatment will begin:
 - - When/if the tumor marker increases to $\geq 70\%$ of the "baseline" level.
OR
 - At the discretion of the treating physician if a patient develops worsening disease-related symptoms with rising tumor marker levels indicating disease progression. In the case of resumption for disease-related symptoms, TKI treatment will continue until the symptoms improve at the discretion of the treating physician and the tumor markers are again $\leq 50\%$ from the level at the time of enrollment.

Study Duration: 48 months

Participant Duration: 48 months

SCHEMATIC OF STUDY DESIGN

2. INTRODUCTION: BACKGROUND INFORMATION AND SCIENTIFIC RATIONALE

2.1 BACKGROUND INFORMATION

Primary thyroid cancers can be classified into 3 groups according to the cells of origin: 1) follicular-cell derived carcinomas which represent 95% of all thyroid cancers and include differentiated thyroid cancers (DTC) such as papillary, follicular and poorly-differentiated thyroid carcinomas; and undifferentiated or anaplastic thyroid carcinomas; 2) parafollicular or C-cell derived carcinomas, termed medullary thyroid carcinomas (MTC) that represent around 4% of all thyroid cancers; and 3) stromal-cell derived carcinomas that represent <1% of all thyroid cancers and include tumors such as thyroid lymphoma, sarcoma or fibrosarcoma. Presently, thyroid cancer exhibits the most rapidly increasing incidence of all solid tumors in the United States and several other countries; and it is already the fifth most common cancer among women in the United States (1-5). During 2017, it is expected that 56,870 patients will be diagnosed with thyroid cancer (6). Despite this rapid increase in incidence, thyroid cancer-specific mortality has remained stable for the last 50 years and most patients with differentiated thyroid cancer have an excellent prognosis with an estimated five-year survival rate > 98% (6). Nonetheless, the five-year survival rate if distant metastases are present is considerably worse (56%), which has also remained unchanged for several decades (6).

In the last decade our understanding of the underlying genetic alterations of thyroid cancer has improved significantly, leading to the development of new therapies (7, 8). Since 2011, the FDA has approved four novel tyrosine kinase inhibitors (TKI) for the treatment of progressive metastatic thyroid cancer: Lenvatinib and Sorafenib for DTC; and Cabozantinib and Vandetanib for MTC).

Lenvatinib is an inhibitor of the vascular endothelial growth factor receptors (VEGFR) 1-3; the fibroblast growth factor receptors 1-4; the platelet-derived growth factor receptor α ; RET; and KIT. In a phase III randomized placebo controlled study (SELECT), Lenvatinib was associated with significant improvements in progression-free survival (18.3 versus 3.6 months) and response rate (64.8% versus 1.5%) (9). Sorafenib is an inhibitor of the VEGFR 1-3, RET, RAF

and platelet-derived growth factor receptor β . In a randomized, double blind, placebo-controlled phase III trial (DECISION), Sorafenib also was associated with a significant increase in progression-free survival (10.8 versus 5.4 months) and response rate (54.1% vs. 33.8%) (10). Cabozantinib, inhibits the hepatocyte growth factor receptor (MET); the vascular endothelial growth factor receptor 2; and RET. In a phase III randomized placebo controlled study (EXAM), Cabozantinib improved the median progression-free survival from 4.0 to 11.2 months (hazard ratio, 0.28 [0.19 to 0.40]); as well as the response rate from 0% to 28% (11). Finally, Vandetanib selectively targets RET, VEGFR and EGFR signaling. In a phase III randomized, double-blind, placebo-controlled study (ZETA), Vandetanib showed to prolong the progression free survival from 19.3 months in the placebo group to 30.5 months in the Vandetanib group (hazard ratio, 0.46 [0.31-0.69]); and to improve the response rate (49% vs 13%) (12). Response to therapy was seen rapidly, at a median of 2 months for radiological response and even earlier for tumor markers in the SELECT study.(9) Most patients on TKI therapy, however, develop resistance to the drug after 12-18 months of treatment, and then tumor restarts progression.(9-12)

TKI therapy has proven to increase the progression free survival; however, their impact on overall survival is still unclear, in part due to the rapid development of tumor resistance. Furthermore, TKI treatment is associated to significant toxicity. Severe (grade 3-4) treatment related adverse events were reported in 76%, 69% and 37% of the patients treated with TKI on the SELECT, EXAM and DECISION studies, respectively, compared to 10%, 33% and 26% in their respective placebo-control groups (9-11). As a consequence of the adverse events, a dose reduction was necessary in 68% of the study participants treated with Lenvatinib, and treatment needed to be interrupted in 82% of patients in the SELECT study (9). Similarly, 64% of the patients required a dose reduction and 66% treatment interruption under Sorafenib treatment in the DECISION trial.(10) In the ZETA study, a significantly higher proportion of patients required dose reduction due to adverse events or QT prolongation in the Vandetanib group than in the placebo group (35% vs. 3%).(12) TKI treatment was permanently discontinued in around 15% of the participants in all studies due to adverse events (9-12).

Finding mechanisms that allow delaying the selection of resistant clones and decreasing the toxicity profile of TKIs in patients with thyroid cancer might improve the progression free survival and could have a positive impact on the overall survival. Adaptive TKI therapy could be one of such mechanisms (13).

2.2 RATIONALE

In general, cytotoxic drugs are administered with the assumption that maximum clinical benefit is obtained by killing the greatest possible number of cancer cells. Consistent with this premise, most systemic cancer chemotherapies are applied at the maximum tolerated dose density. This model is being theoretically challenged by an alternative model that views cancer therapy as an evolutionary and ecological process (13, 14). This alternative model rests on three major assumptions. First, phenotypically or environmentally mediated resistant cells are present before treatment. Second, most xenobiotic mechanisms protecting cells from cytotoxic agents do not require mutations, but rather increased expression of molecular machinery already encoded in the genome. Third, cancer populations within a tumor compete with each other for space and substrate. Clearly, in the presence of chemotherapy, resistant cells are better adapted and, thus, fitter (more proliferative) than wild-type cells. However, in the absence of chemotherapy, this fitness difference is typically reversed because of the metabolic cost of the resistance mechanism (synthesis, maintenance, and operation of membrane extrusion pumps). In an environment of limited substrate, this cost requires diversion of resources from proliferation and invasion. In this Darwinian setting, maximum dose density therapy strongly selects for resistant phenotypes and, by removing all competitors, permits

unconstrained proliferation of the resistant populations even when no drug is present—a phenomenon well recognized in evolutionary dynamics as “competitive release”.

A recent study applied these evolutionary principles to prolong tumor control in preclinical models of breast cancer (15). In this study, mice with orthotopic implants of breast cancer cells survived longer using a treatment regimen that modulated the dose according to changes in tumor volume than those receiving standard chemotherapy. One of the limitations to translate this into the clinical practice is that tumor volume was evaluated twice a week through MRI. However, in thyroid cancer, there are specific tumor markers (thyroglobulin for DTC and calcitonin for MTC) that have a direct correlation with the burden of disease (16, 17). Therefore, these biomarkers can be used as an indirect reflection of the response to therapy to adjust treatment dose.

2.3 POTENTIAL RISKS AND BENEFITS

2.3.1 KNOWN POTENTIAL RISKS

Potential risks for study participants for both adaptive TKI therapy and conventional TKI therapy are related to TKI side effects (See section 8 and Appendix 3).

Additionally, the efficacy of adaptive TKI therapy for the treatment of advanced progressive thyroid cancer is currently unknown. Therefore, there is the potential of disease progression. Study participants will be monitored closely with regular clinical examination, tumor marker measurement, and imaging studies so that progression is detected early if present. If it occurs, the treatment will be modified accordingly.

2.3.2 KNOWN POTENTIAL BENEFITS

Lenvatinib and Sorafenib in patients with advanced progressive differentiated thyroid cancer and Cabozantinib, and Vandetanib in patients with advanced progressive medullary thyroid cancer have proven to increase the progression free survival in phase 3 randomized controlled trials (9-12).

3. OBJECTIVES AND PURPOSE

Primary objective:

- To evaluate the efficacy and tolerability of TKI therapy (Lenvatinib or Sorafenib for DTC; Cabozantinib or Vandetanib for MTC) through adaptive (intermittent) versus conventional (continuous) regimen.

Secondary objective:

- To evaluate response and survival of TKI therapy (Lenvatinib or Sorafenib for DTC; Cabozantinib or Vandetanib for MTC) through adaptive (intermittent) versus conventional (continuous) regimen.

Exploratory objective:

- To determine predictive biomarkers of TKI response.

4. STUDY DESIGN AND ENDPOINTS

4.1 DESCRIPTION OF THE STUDY DESIGN

This is a pilot randomized phase 2 clinical trial to evaluate the efficacy and tolerability of TKI therapy through adaptive (intermittent) versus conventional (continuous) regimen in patients with DTC or MTC. Eligible subjects with DTC or MTC will have measurable disease according to Response Evaluation Criteria in Solid Tumors (RECIST 1.1) and will be randomized 2 to 1 to receive adaptive (intermittent) versus conventional (continuous) therapy when and if the tumor marker drops 50% or more from the baseline level (before initiating TKI treatment) within the first two months of treatment. Randomization will be stratified by cancer types, DTC vs. MTC. Patients in which the tumor marker does not drop by 50% or more within 2 months (“non-responders”) will be kept on conventional therapy and used to compare with the patients who drop their tumor markers by 50% or more as an exploratory analysis.

All patients will start receiving standard of care treatments: Lenvatinib 24 mg daily or Sorafenib 400 mg twice daily with DTC; Cabozantinib 140 mg daily or Vandetanib 300 mg daily with MTC. Doses will be adjusted as needed due to toxicity or drug tolerance in both arms (See section 6.1.8).

- Patients in the conventional therapy regimen (“responders” and non-responders”) will receive continuous (daily) treatment at the indicated dose.

- Patients in the adaptive therapy regimen will receive TKI therapy in cycles: continuous (daily) treatment at the indicated dose until the patients’ tumor marker (thyroglobulin in DTC patients; calcitonin or CEA in MTC patients) drops by $\geq 50\%$ from the level at the time of enrollment (“baseline” level). $\geq 70\%$ of Only tumor markers that meet inclusion criteria at baseline can be used for randomization and adaptive therapy purposes. A new cycle of TKI treatment will begin:

1. When/if the tumor marker increases to $\geq 70\%$ of the “baseline” level.
OR
2. At the discretion of the treating physician, if a patient develops worsening disease-related symptoms with rising tumor marker levels indicating disease progression. In the case of resumption for disease-related symptoms, TKI treatment will continue until the symptoms improve at the discretion of the treating physician and the tumor markers are again $\leq 50\%$ from the level at the time of enrollment.

All study participants will be followed for at least 24 months after treatment initiation. Patients will continue to receive treatment until confirmed disease progression, development of unacceptable toxicity, withdrawal of consent, or study termination by investigator. After disease progression, subjects will be followed for survival and may be treated according to standards of care, which includes conventional (continuous) TKI treatment for patients in the adaptive therapy arm.

After 24 months, patients in the adaptive therapy arm that remain on TKI therapy and under control will be given the choice to continue with adaptive therapy or to convert to conventional (continuous) regimen, which is the current standard of care.

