10.3 DESCRIPTION OF STATISTICAL METHODS

10.3.1 ANALYSIS OF THE PRIMARY EFFICACY ENDPOINT(S)

The primary endpoint is the time-to-discontinuation of treatment.

- The measurement endpoint is the status of a patient 12 months following the start of TKI.
- This is a binary metric. 1 = the patients is still receiving TKI at 12 months; 0 = patient is no longer on TKI due to cancer progression and/or toxicity.
- The results will be described as % patients that remain on TKI at 12 months by experimental and control groups.
- The test statistic will a Fisher's Exact test on a two by two contingency table of patient counts based on all four combinations of whether a patient remains or does not remain on TKI (0 or 1) by treatment group (adaptive therapy or continuous therapy)
- We will begin by comparing the historical control patients with the control patients of the trial. If these two groups do not differ (using a Type I error rate of $p > 0.1$) then they shall be combined to provide the patient counts for the Fisher's Exact Test comparison of the control group to the experimental group of the trial.
- If the historical control patients differ from the control patients of the trial (using a Type I error rate of $p < 0.1$) then they will be compared separately to the experimental group using Fisher Exact test's with a Bonferroni adjusted Type I error rate of $p < 0.05$.

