10.4 SAMPLE SIZE

The planned study is a randomized clinical trial, with 2:1 randomization to adaptive therapy versus conventional therapy. The primary endpoint is time-to-discontinuation (TTD) of treatment, which is a “survival analysis”-type statistical comparison. We plan to enroll 24 patients on the adaptive therapy and 12 on the conventional therapy arm. Assuming uniform enrollment of patients for 2 years, with a minimum follow-up of 2 years, and a one-sided $\alpha = 0.20$, we will have 82% power to detect a hazard ratio of 0.50, assuming 12 and 24 month median TTD for the conventional and adaptive therapy groups. If the median TTD of the adaptive group is 20 months (HR=0.6), the power is 67%.

We anticipate that 20% of the patients will not have the $\geq 50\%$ drop in tumor markers needed for study randomization arm of the study. Thus, we anticipate recruiting ~45 patients to have 36 patients for randomization.

Objective time-to-discontinuation criteria are described in Section 4.2.1. Patients may electively withdraw from treatment at any time and will be counted as a discontinuation event. All randomized patients will be included in the primary analysis. A sensitivity analysis will also be conducted, where the patients who choose to withdraw are considered as censored (non-events) at the time of withdrawal.

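### Randomization is stratified by DTC/MTC, but no primary analysis uses the stratum: a minor mismatch, fixable by wording, with little effect on power at N = 36

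*Combined protocol and SAP*

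**What the plan says.** Section 4.1 sets 2:1 allocation with cancer type as the only stratification factor: "Randomization will be stratified by cancer types, DTC vs. MTC".

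Section 10.3.1 reduces the primary endpoint to on or off TKI at 12 months. It tests this with Fisher's "Exact test on a two by two contingency table of patient counts", arm by status, with no stratum. It also adds historical controls to the trial controls when the two groups do not differ at the 0.1 level, again without regard to cancer type.

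Sections 10.1 and 10.4 call the same endpoint a survival-type comparison and power it that way: "We plan to enroll 24 patients on the adaptive therapy and 12 on the conventional therapy arm". At a one-sided level of 0.20 they claim 82% power for a halved hazard, taking medians of 12 months (conventional) and 24 months (adaptive). They name no test. No statistical section uses cancer type in any analysis.

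The documents give no expected DTC/MTC split, no assumed difference in time to discontinuation between the cancers, and neither the number nor the cancer mix of the historical controls.

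**The concern.** A factor worth stratifying on is presumably one expected to matter, and the usual practice is to carry it into the analysis. Section 2.1 gives some reason to think it could matter. It cites median progression-free survival on treatment of 18.3 months (lenvatinib) and 10.8 months (sorafenib) for DTC, and 11.2 months (cabozantinib) and 30.5 months (vandetanib) for MTC.

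If prognosis differs, balancing the arms by stratum and then ignoring it makes a pooled test's error rate depend on the size of that difference. With 36 randomized patients and a stated power of only 67% at HR 0.6, any avoidable loss deserves a check. The historical-control step adds a second exposure, because stratified randomization does nothing to balance patients who were never randomized.

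**Working it through.** **1. Reproduce the stated power.** Inputs from section 10.4: 12 and 24 patients, medians 12 and 24 months, 24 months' uniform accrual, at least 24 months' follow-up, one-sided 0.20.

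Event probability with exponential times: p = 1 − (e^(−24λ) − e^(−48λ))/(24λ), λ = ln 2/median.

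- Conventional: 1 − (0.25 − 0.0625)/1.386 = 0.865, times 12 = 10.4 events.
- Adaptive: 1 − (0.50 − 0.25)/0.693 = 0.639, times 24 = 15.3 events.
- Total: 25.7 events.

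Wald power for the log hazard ratio: SE = √(1/10.38 + 1/15.34) = 0.402; Φ(0.693/0.402 − 0.842) = Φ(0.883) = 81.1%. A simulated unstratified log-rank gives 81.2%, and Freedman's formula with 2:1 allocation 82.9%. The stated 82% is therefore that of an unstratified time-to-event test.

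**2. Log-rank, unstratified against stratified, HR 0.50.** Simulated, assuming 24 DTC and 12 MTC patients, 2:1 within each stratum, follow-up of 24-48 months, and each arm's cited median standing in for the control median.

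| Control medians, DTC/MTC (months) | Size, unstratified | Size, stratified | Power, unstratified | Power, stratified |
|---|---|---|---|---|
| 10.8 / 30.5 | 19.0% | 21.3% | 75.0% | 77.6% |
| 18.3 / 11.2 and 18.3 / 30.5 | – | – | gain from stratifying: 0 to 0.4 points | |
| 10.8 / 11.2 | – | – | 81.7% | 81.0% |
| 12 / 12 | 21-22% | 21-22% | 81.2% | 80.4% |

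In the first row the nominal gain is 77.6 − 75.0 = 2.6 points, but size rises by 21.3 − 19.0 = 2.3 points. With both tests calibrated to a true 20%, power is 76.1% for each. With follow-up capped at 24 months, the calibrated figures are 72.9% unstratified and 72.2% stratified.

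**3. Sensitivity to the assumed mix and gap.** With 30 DTC and 6 MTC patients, the first-row contrast falls to 78.5% against 79.9%. A wider grid took the MTC share as 1/6, 1/3 or 1/2 and held the control rate at 12 months at 50%. The nominal gain is nil at a 1.5-fold ratio of medians, up to about 1.5 points at twofold, and 1.5 to 5 points at threefold. Over the threefold cells the unstratified size is 18-21% and the stratified size 21-22%, so part of that gain is again size.

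**4. The test actually written.** Proportions on treatment at 12 months are 0.50 and 2^(−1/2) = 0.71. Section 10.3.1 gives no level for the pooled Fisher comparison, so one-sided 0.20 is carried over from 10.4. Randomized patients only, over the same grid:

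| MTC:DTC median ratio | Fisher size | Exact stratified size | Fisher power | Exact stratified power |
|---|---|---|---|---|
| 1 | 10.2-10.4% | 11% | about 52% | 52-53% |
| 2 | 9.5-10.0% | 12% | about 51% | 52-53% |
| 3 or 1/3 | 8.6-9.8% | 12-13% | 49-51% | 51-53% |

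Fisher's size is already about 10% when the cancers have identical prognosis, so most of its conservatism is discreteness. Omitting the strata takes off at most a further 10.4 − 8.6 = 1.8 points.

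**5. Historical controls.** Assumed: MTC one third of the trial, MTC median 2-3 times the DTC median, 20-40 historical controls, nominal one-sided 0.20 after pooling, and the trial controls alone tested at 0.05 when pooling is refused. Overall error is 21-31% if the historical controls are all DTC, 11-14% if they have the trial's mix, and 3.5-7.5% if two thirds are MTC.

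**The case against.** The strongest case against is that stratifying buys nothing measurable here. At equal size the widest cited pair shows no gain, and the other pairs show little or none even at the nominal level. Nor does the stratified log-rank come closer to 20% in that widest pair: 21.3% is further away than 19.0%. This stands. What stratifying offers is a size that hardly moves with the prognosis gap and an analysis that matches the allocation.

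A reader might infer from section 2.1 that cancer type is shown to be prognostic. The documents do not support that. The medians are progression-free survival by drug from separate trials, and the DTC and MTC ranges overlap. The placebo medians in the two MTC trials, 4.0 and 19.3 months, show that those populations are not comparable. A 30.5-month control median also sits badly with the plan's own assumption of 12.

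A reader might also infer that the omission makes the primary test conservative. That holds only for the randomized comparison under a material gap, and there mainly through Fisher's discreteness. Once historical controls are pooled, the error can go either way. Finally, sections 10.1 and 10.4 cannot be said to specify an unstratified test, because they name none.

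**Conclusion.** The mismatch is real and minor. Allocation is stratified by cancer type, the written primary test is not, and no other section supplies a stratified one. The consequence is an error rate that shifts by 2 to 3 points across plausible prognosis gaps, with a power effect between about 1 point lost and about 3 points gained at the nominal level for the cited medians. A claim of material power loss is not supported. The step where ignoring cancer type could do most harm is the historical pooling, where it amounts to confounding.

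The larger loss is a separate matter: about 81% power for the time-to-event comparison against about 52% for Fisher at 12 months.

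The sizes rest on exponential times, an assumed DTC:MTC mix, assumed ratios of medians, and assumed numbers and mixes of historical controls. The mismatch itself rests only on the text.

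**What to change.** In section 10.3.1, make the primary test a log-rank test stratified by DTC/MTC, state its one-sided level, and take the hazard ratio from a Cox model stratified the same way. This also aligns the test with the endpoint that was powered. If the 12-month binary summary is kept, use an exact stratified (Mantel-Haenszel-type) test. If historical controls are retained, compare and pool them within cancer type.

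The cost is wording only, since the stratum is recorded at randomization; for historical controls, cancer type must be available. The downside is about 1 point of power if the two cancers do not differ, and an asymptotic size of about 21-22% at nominal 20%. A permutation p-value computed within strata removes the excess.
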